8.4.3 Per Protocol Analysis Set

The Per Protocol Analysis Set (PP) is defined as all subjects in the FAS who do not have any major protocol violations, including:

- Violations of inclusion/exclusion criteria;

- Use of prohibited concomitant medications;
- Noncompliance (ie, <80% compliant with study treatment);
- Failure to provide a clinical observation at Week 5 (\pm 2 day, Visit 7);

The PP will be a secondary population used for efficacy analysis.

8.4.4 Safety Analysis Set

The Safety Analysis Set is defined as all enrolled who received at least one dose of study treatment.

8.5 Planned Methods of Analysis

8.5.1 Background and Demographic Characteristics

Descriptive statistics will be used to summarize demographic characteristics (age, gender, and race) and background characteristics for the enrolled subject population.

Past/coexistent medical history information for all subjects will be presented in a by-subject listing.

8.5.2 Study Product/Visit Compliance

The number and percentage of subjects attending each study visit will be presented. Compliance to study treatment and extent of exposure will be summarized by descriptive statistics of total number of uses, total weight of product used, and average weight per application of product. The number and percentage of subjects who received fewer than 80% will be presented.

8.5.3 Prior and Concomitant Therapy

Prior and concomitant medication information for all treated subjects will be presented in a by-subject listing.

8.5.4 Efficacy Analysis

The primary data analysis set for efficacy analyses will be the PP defined in Section 8.4.3. The primary analysis will be the determination of the severity and intensity of mucositis from Baseline to Visit 7 (Day 36).

The secondary efficacy endpoints analysis will be summarized using standard statistical methods and outlined in the Statistical Analysis Plan (SAP). In general, categorical endpoints will be tabulated by number, percentage, and a 95% 2-sided confidence interval (exact methodology) will be estimated. Continuous endpoints (i.e., percent change from baseline) may be summarized using descriptive statistics (N, mean, median, standard deviation, and range).

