4. SELECTION OF STUDY POPULATION

4.1 Number of Subjects Required

An estimated number of 15 patients at least 18 years of age will be enrolled in this study to ensure 10 analyzable patients who complete the study. Dropouts secondary to poor compliance or patients who have more than two weeks of radiation treatment break will be excluded and will be replaced by enrolling more patients.

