6.6 Subject Replacement

Subjects who prematurely discontinue the study will not be replaced. Up to 15 subjects will be enrolled to ensure 10 subjects complete the trial.

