7.6.1 Pain Assessment

At each Study Visit the NRPS will be recorded for mouth pain and pain upon swallowing. For the primary efficacy assessment the NRPS scale at baseline will be compared to Week 5. Subjects that complete at least 80% of treatments as determined by the diary and confirmed by the weight of the returned study product will be included in the efficacy analysis.

If possible, the same investigator who completes the scoring at Baseline should complete all subsequent assessments for the patient.

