8.4.2 Full Analysis Set

The Full Analysis Set (FAS) is defined as all subjects who receive at least one administration of the investigative study regimen and who had at least one post-Baseline efficacy assessment. The FAS population will be the primary population used for efficacy analysis.

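### Sections 8.4.2 and 8.4.3 make the FAS the primary efficacy set, Section 8.5.4 makes it the PP set, and nothing says which prevails

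*Combined protocol and SAP*

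**What the plan says.** The statistical section assigns the roles of the analysis sets in three places:

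- Section 8.4.2: "The FAS population will be the primary population used for efficacy analysis". Membership requires at least one administration of the regimen and is limited to patients "who had at least one post-Baseline efficacy assessment".
- Section 8.4.3: "The PP will be a secondary population used for efficacy analysis". The PP set is the FAS less major violations. Those named are eligibility violations, prohibited concomitant medication, compliance below 80% and no clinical observation at Week 5 (Visit 7).
- Section 8.5.4: "The primary data analysis set for efficacy analyses will be the PP defined in Section 8.4.3".

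Three other sections also bear on who is analysed or enrolled:

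- Section 7.6.1, on the primary pain comparison, admits to the efficacy analysis "Subjects that complete at least 80% of treatments as determined by the diary", with confirmation from the weight of returned product.
- Section 4.1: "Dropouts secondary to poor compliance or patients who have more than two weeks of radiation treatment break will be excluded and will be replaced".
- Section 6.6: "Subjects who prematurely discontinue the study will not be replaced". Sections 6.6 and 8.1 both set enrolment at up to 15, so that 10 complete. Section 4.1 calls 15 an estimate and provides for further enrolment.

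**The concern.** Section 8.5.4 names as primary the set that the section it cites calls secondary. An analyst can produce results for both sets but cannot tell from the plan which one leads.

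This matters because there is no concurrent control. Section 3.1 says overall efficacy is determined by comparison with historical controls, so the patients in the leading set determine the figure that is compared. The study is open-label, and with two sets each named primary, the choice can follow the results.

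The sets also differ in ways that may relate to outcome. Three of the PP criteria act after baseline: compliance below 80%, prohibited concomitant medication and no Visit 7 observation. The radiation-break exclusion in Section 4.1 is a fourth post-baseline criterion, outside both definitions. Section 1.1 links mucositis to reduced treatment compliance and to radiation breaks, so selection bias is possible.

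**Working it through.** **1. The passages side by side**

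| Section | FAS | PP set | Other rule |
|---|---|---|---|
| 8.4.2 | primary | – | – |
| 8.4.3 | – | secondary | – |
| 8.5.4 | – | primary | – |
| 7.6.1 | – | – | at least 80% of treatments |
| 4.1 | – | – | excludes poor-compliance dropouts and radiation breaks over two weeks |

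The first three rows cannot all hold. The references to a separate statistical analysis plan do not settle the matter: Section 3.1 defers only additional secondary and exploratory endpoints, and Section 8.5.4 only the secondary endpoint analysis.

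Section 7.6.1 conflicts with a FAS primary analysis, because the FAS has no compliance threshold. It does not reproduce the PP set either, because it omits the other three criteria of Section 8.4.3.

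The radiation-break criterion of Section 4.1 appears in neither Section 8.4.2 nor Section 8.4.3. As those definitions stand, both sets keep such patients. Correcting Section 8.5.4 alone would therefore leave the denominator open.

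On replacement, Section 4.1 conflicts with Section 6.6 for poor-compliance dropouts. For patients with a long break the conflict is less clear, because they need not have discontinued.

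**2. How far apart the two sets could be**

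The plan has no power calculation to reproduce; Section 8.2 says the study is not powered. From the documents: 15 enrolled and 10 completing (Sections 4.1, 6.6 and 8.1), an implied loss of up to 5/15 = 1/3, and exact 95% intervals for categorical endpoints (Section 8.5.4).

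Assumptions: 10 patients qualify for the PP set, 15 are in the FAS, and all 15 have a Visit 7 value. The five outside the PP set then fall out for reasons other than a missing Visit 7. The event is any yes/no outcome at Visit 7, for example RTOG grade 3 or higher. It is illustrative and not an endpoint of the plan.

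With x events among the 10 PP patients, the FAS rate is lowest if none of the other five has the event and highest if all do:

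x/15 ≤ FAS rate ≤ (x + 5)/15

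| PP rate | Lowest FAS rate | Highest FAS rate |
|---|---|---|
| 3/10 = 30% | 3/15 = 20% | 8/15 = 53% |
| 5/10 = 50% | 5/15 = 33% | 10/15 = 67% |
| 7/10 = 70% | 7/15 = 47% | 12/15 = 80% |

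If only 12 patients were in the FAS, 5/10 would be compatible with 5/12 (42%) to 7/12 (58%). If the patients outside the PP set do not differ from those inside, or have no Visit 7 value, the observed results agree.

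Exact (Clopper-Pearson) 95% intervals, for scale:

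- 5/10: 18.7% to 81.3%
- 5/15: 11.8% to 61.6%
- 10/15: 38.4% to 88.2%

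**The case against.** The strongest reply is that little hangs on the choice. The study is small, descriptive and unpowered, so no test or alpha is affected. Sections 8.4.2 and 8.4.3 already give both sets an efficacy role, so both can be reported. Section 8.5.2 reports how many patients fall below 80%, which makes a late choice partly visible. The exact interval for 5/10 is wider than the range between the sets.

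Most of that stands, and it limits the consequence. It does not remove the problem: partial visibility does not prevent a late choice, and sampling uncertainty does not settle which estimate is put beside the historical controls.

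It can also be said that Section 7.6.1 favours a PP-type analysis. That is true, and it means the documents do not compel the FAS. They compel a decision.

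A reader might infer more than the documents support, in four ways:

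- **That the PP set flatters the product.** Dropping patients who do badly would have that effect, but no section gives the outcomes of those who would be dropped. Section 1.1 speaks of treatment compliance in general, not of compliance with the rinse.
- **That the FAS is free of selection.** It requires one post-baseline efficacy assessment. The ITT set has no such condition, but no section gives it an efficacy role, and its extra patients have no post-baseline value to analyse.
- **That radiation breaks separate the two sets.** Neither definition contains that criterion.
- **That enrolment is open-ended.** Section 4.1 alone could be read so, but Sections 6.6 and 8.1 both say up to 15.

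**Conclusion.** The contradiction between Sections 8.4.2 and 8.4.3 on one side and Section 8.5.4 on the other is certain and must be corrected. It rests on current text and needs no assumption. The conflicts with Sections 7.6.1 and 4.1 are equally textual.

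The size of the effect is not known. In the illustration, moving from the PP set to the FAS shifts a 50% rate by at most about 17 percentage points either way. That rests on the assumed 10 and 15 patients and on complete Visit 7 data. Selection bias is possible, but neither its direction nor its size can be derived. What is at stake is which estimate leads the comparison with historical controls.

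The FAS is the better choice for the primary set, because two of the three sections that assign roles support it and it has fewer post-baseline exclusions. That is a recommendation, not something the documents dictate.

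**What to change.** Before any data are reviewed:

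1. Name one primary set. Recommended wording for Section 8.5.4: *The FAS (8.4.2) is the primary set for efficacy; the PP set (8.4.3) is supportive.* Report both.
2. In Section 7.6.1, apply the 80% restriction to the PP set only.
3. State that Section 4.1 does not remove patients from the FAS. If the radiation-break exclusion is kept, list it among the PP criteria in Section 8.4.3 and report how many patients it affects.
4. Reconcile Section 4.1 with Sections 6.6 and 8.1, both on replacement and on whether 15 is a limit.
5. For each set, report observed cases at Visit 7 with the number missing.

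The cost is small: wording edits in the sections named and a few counts in the efficacy tables. The leading result may move in either direction, and the sponsor should accept that it may be less favourable.

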8.5.5 Safety Evaluations

Adverse events

The assessment of safety will be based on the frequency of AEs and the severity of AEs according to the CTCAE Version 4.

Adverse events may be summarized by Medical Dictionary for Regulatory Activities (MedDRA) system organ class and preferred term. Adverse events will be summarized by presenting, for each treatment group, the number and percentage of subjects having any AE, having an AE in each body system and having each individual AE. Any other information collected (e.g., severity or relatedness to study medication) will be listed as appropriate.

8.6 Interim Analyses

No interim analyses are anticipated.

9.0 ADMINISTRATIVE PROCEDURES

9.1 Ethics and Good Clinical Practice

This study must be carried out in compliance with the protocol and in accordance with standard operating procedures (SOP) of the clinical site.

9.1.1 Institutional Review Board (IRB)

Before implementing this study, the study site must determine if this study requires local IRB approval of the protocol, the proposed informed consent form. If required a signed and dated statement that the protocol and informed consent form have been approved by the IRB must be received before study initiation. All IRB procedures must be followed e.g.

approval of the informed consent document, advertising materials, any amendments to the protocol, other than administrative ones, and the reporting of serious adverse events.

9.1.2 Subject Information and Consent

The investigator or designee must explain to each subject the nature of the study, its purpose, the procedures involved, the expected duration, the potential risks and benefits involved, and any discomfort it may entail. Each subject must be informed that participation in the study is voluntary, that he/she may withdraw from the study at any time, and that withdrawal of consent will not affect his/her subsequent medical treatment or relationship with the treating physician.

This informed consent should be given by means of a standard written statement, written in non-technical language. The subject should read and consider the statement before signing and dating it, and he/she should be given a copy of the signed document. No subject can enter the study before informed consent has been obtained from him or her.

9.1.3 Confidentiality

All records identifying the subject will be kept confidential and, to the extent permitted by the applicable laws and/or regulations, will not be made publicly available.

Subject names will not be supplied to the sponsor. Only the subject number will be recorded in the CRF, and if the subject name appears on any other document it must be obliterated before a copy of the document is supplied to the sponsor. As part of the informed consent process, the subjects will be informed in writing that representatives of the sponsor, IRB, or regulatory authorities may inspect their medical records to verify the information collected, and that subject confidentiality will be maintained at all times.

9.2 Changes in the Conduct of the Study or Planned Analyses

9.2.1 Protocol Amendments

With the exception of administrative changes, any changes or additions to this clinical study protocol require a written protocol amendment that must be approved by the Sponsor and the investigator before implementation.

9.2.2 Other Changes in Study Conduct

Deviations from the planned study conduct are not permitted; any unforeseen changes in study conduct must be reported within 5 days to the sponsor.

9.2.3 Termination or Suspension of Study

The sponsor reserves the right to terminate or suspend the study at any time. If applicable, the IRB will be notified of the termination/suspension and the reason(s).

9.3 Data Handling and Record Keeping

9.3.1 Recording of Data

Case report forms will be designed to identify each subject by number and subject's initials, the protocol number, and the results observed. Data on subjects collected on CRFs during the study will be documented and properly coded, and the subject will only be identified by the subject number, and by his/her initials, if also required. If, as an exception, it is necessary for safety or regulatory reasons to identify the subject, both the study sponsor, and the investigator are bound to keep this information confidential.

All CRFs must be completed legibly and accurately using a black ballpoint pen. Pencils and correction fluids may not be used. If corrections are necessary, an authorized member of the investigator's staff will enter them in the following manner: the wrong entry will be crossed out (however, it must remain legible) and the correct entry will be placed next to it. Corrections will be initialed and dated. The CRFs will be kept in order and current, so that they reflect the latest observations on the subjects enrolled in the study.

In addition to the case report forms, individual subject source documents will be maintained. These documents may include the visit dates, the clinical study number, the name or initials of the subject, medical history or previous physical examinations, demographic and medical information, including, concomitant medications/treatments, etc, any AEs encountered, and other notes, as appropriate. All information on CRFs must be traceable to the source documents kept in the subject's file, including reasons for corrections on the CRF or source documents. These reasons must be initialed and dated by the individual who made the correction. Data without a written or electronic record will be defined before the start of the study and will be recorded directly on the CRFs by the investigator or his/her designee, which will be documented as being the source data.

The lead investigator at each site must sign the designated page(s) of the CRFs, thereby stating that he/she takes responsibility for the accuracy of the data in the entire case record book. All records will be kept in conformance to applicable U.S. laws and regulations.

The original signed informed consent form will be attached to each subject's file. When the study treatment is completed, the informed consent form will be in the appropriate file folder; otherwise a note indicating where the records can be located will be made.

9.3.2 Retention of Documents

Essential documents, as listed below, must be retained in a secure place by the investigator for a minimum of 5 years from completion of the study (and must inform the Sponsor prior to destruction), or as long as needed to comply with national and international regulations (generally 2 years after discontinuing clinical development or after the last marketing approval). The investigator agrees to adhere to the document retention procedures by signing the protocol. Essential documents include:

- the study protocol and any amendments;
- IRB approvals for the study protocol and all amendments;
- all source documents;
- CRF originals or copies;
- subjects' informed consent forms (with study number);
- Product inventory
- any other pertinent study document (e.g., investigator's brochure, correspondence, study reports, etc.).

9.3.3 Database Management

Data will initially be entered into an acceptable database for review and analysis.

9.3.4 Coding of Concomitant Medications and Adverse Events

Concomitant medications entered into the database may be coded using the World Health Organization (WHO) Drug Reference List which classifies the medications according to the Anatomic Therapeutic Chemical classification system. Coexistent diseases and AEs may be coded using the Medical Dictionary for Regulatory Activities (MedDRA).

9.3.5 Database Lock

When the database has been declared to be complete and accurate, the database will be locked.

9.4 Product Handling and Accountability

All product supplies are to be used only for this clinical study and not for any other purpose. Study product supplies must be kept in an appropriate, secure area (eg, locked cabinet) and stored according to the conditions specified on the product labels.

The investigator site must maintain a full record of the shipment and dispensing of study product in a product accountability ledger. This log must be kept current and should contain the following information:

- identification of the subject to whom the study product was dispensed,
- date(s) and quantity of the study product dispensed to the subject,
- date(s) and quantity of the study product returned by the subject (if applicable), and
- initials of the study site representative(s) dispensing and receiving returned study product.

The inventory must be available for inspection by the study monitor. Any discrepancy and/or deficiency must be accounted for.

The investigator must not destroy any product labels, or any partly used or unused product supply. At the conclusion of the study and, as appropriate, during the course of the study, all study product supplies, including partially used or empty containers, must be returned or destroyed according to the designation of the sponsor. Any missing supplies will be indicated on the inventory.

If requested in writing by the sponsor, unused product supplies may be destroyed by the Principal Investigator, provided such disposition does not expose humans to risks from the drug. **Records shall be maintained by the principal investigator of any such alternative disposition of the investigational product.** These records must show the identification and quantity of each unit disposed of, the method of destruction (taking into account the requirements of local law), and the person who disposed of the products. Such records will be retained in the principal investigator's records for this clinical study and copies will be submitted to the sponsor.

9.5 Quality Control and Quality Assurance

9.5.1 Monitoring Procedures

During the study, a study monitor may visit the study site(s) regularly to check the completeness of subject records, the accuracy of entries on the CRFs, adherence to the protocol and to the principals of ICH-GCP guidelines, the progress of enrollment, and also to ensure that study product is being stored, dispensed, and accounted for according to specifications. Key study personnel must be available to assist the study monitor during these visits.

The data required by the protocol must be recorded on the appropriate CRFs. The CRFs and any source documents will be available to the study monitor who will perform a 100% data check (comparison of the data recorded in the CRF with those in the source documents). The CRFs and source data will also be available for an audit by the sponsor, or sponsor representative, at any time.

The investigator must give the monitor and auditor access to relevant hospital or clinical records, to confirm their consistency with the CRF entries. No information in these records about the identity of the subjects will leave the study site(s). Additional checks on the consistency of the source data with the CRFs are performed according to the study-specific monitoring plan. The completed CRFs and all other records will be kept on file as outlined above (see Section 9.3.2 on retention of documents).

9.5.2 Auditing Procedures

In addition to the routine monitoring procedures, a study center may be audited in depth for study quality assurance by the sponsor, an external auditor on behalf of the sponsor, and/or by regulatory authorities. This audit may include a review of all source documents, drug records, and original CRFs at some or all of the study sites used in the study. Subject confidentiality will be maintained at all times and consent for this will be obtained before

entry of the subject into the clinical trial (see Section 8.1.2 on informed consent). If an inspection is requested by a regulatory authority, the investigator must immediately inform the study sponsor that this request has been made.

